8.2 Analysis Sets

The following analysis sets will be used to address the specific protocol objectives.

Screened Analysis Set (SAS): The screened analysis set consists of subjects treated at least once in the parent study who signed the informed consent to participate in the LTE study. This is the analysis set for presenting LTE baseline information and the status of subject participation in the LTE study.

Safety (SAF) Analysis Set: The safety analysis set includes all subjects enrolled in the LTE who received at least one dose of treatment during the LTE. This analysis set is the primary analysis set used for all safety summaries.

Full Analysis Set (FAS): The full analysis set includes all subjects enrolled in the LTE who received at least one dose of treatment during the LTE and have at least one post-LTE entry effectiveness measure recorded. This analysis set is the primary analysis set used for all effectiveness analyses.

8.3 Treatment Exposure, Estimated Number of Subjects in Group Comparisons of Interest

LTE-eligible subjects from the Phase 2b and Phase 3 parts of the parent study will complete 24-weeks of treatment as part of that study, additional weeks of treatment under the same active treatment arms as they enter LTE and until they start optimal dosing once this dose is identified at the end of Phase 2b.

LTE-eligible subjects from the Phase 2b and Intermediate Parts of the parent study who are randomized to placebo will be re-randomized in a blinded manner to any of the active treatment dose groups at LTE entry and prior to being treated with the optimal dose at the end of Phase 2b. Depending on the timing of their enrollment and initial treatment in the Intermediate part of the study, treatment duration under the parent study will be at least 24 weeks prior to being treated

with the optimal dose at the end of Phase 3. The actual duration of treatment during the parent study, during the waiting period for the optimal dose and during the LTE, will be reported.

LTE subjects will be treated at different dose levels prior to the optimal dose being identified. In addition, duration of treatment under the parent dose among those in the Phase 2b and Intermediate Parts may vary before the optimal dose is identified at the end of Phase 2b. Thus time-varying treatment exposure is a key characteristic of the combined parent and LTE trials and will be considered in describing levels and trends in safety and effectiveness endpoints recorded during the LTE trial.

The actual number of subjects by LTE treatment groups will be reported. Summary descriptive statistics will be reported for dose intensity and relative dose intensity by LTE treatment groups. Patterns of continuous dose intensity will be described by fitting a polynomial regression with dose intensity as a response variable and weeks in the study as polynomial splines. In addition, levels and patterns of dose intensity (and relative dose intensity) over LTE time intervals will be described.

8.4 Baseline and Demographics and Subject Study Disposition

With exception of the delayed-start analysis, for both the efficacy and safety analyses, baseline will be defined as the time prior to starting active treatment with AV-101 in either the LTE or the parent study. For Groups 1 and 2, since the subjects start receiving active treatment in the parent study, the baseline will be the values prior to first dose during the parent trial. For Groups 3 and 4, the subjects receive placebo in the parent trial and then receive active treatment in the LTE study, thus, the baseline will be the values prior to the first dose in LTE study.

Demographics and baseline data, medical and surgical history will be summarized using the screened analysis set. These demographics and baseline data will be presented by the LTE treatment groups as described in [Section 8.1](#).

Demographic and baseline data will be summarized using summary statistics of mean, standard deviation, median, lower quartile, upper quartile, min and max for continuous variables and number and percentage of subjects in each category.

Subject treatment status and study participation status will be reported for the safety analysis set. Subjects who completed all LTE assessments and early treatment discontinuation and withdrawal from the study including reasons for treatment or study discontinuation will be reported by LTE treatment groups.

8.5 Effectiveness Analyses

Descriptive summary statistics will be reported for each effectiveness endpoint by LTE treatment groups. The FAS will be used as the analysis set. Comparisons of levels in effectiveness endpoints at specific visits (e.g. Week 24 after LTE baseline) among LTE treatment groups will be performed using statistical models applicable to the measurement scale (continuous, categorical, time-to-event). Tests of hypotheses in these models will be performed with two-sided tests at 0.05 significance level, adjusted for multiple comparisons. Effectiveness endpoints among Group 1

subjects will be compared with subjects in Group 4, Group 3, and Group 2. Associated 95% confidence intervals for the difference in outcomes in pairwise treatment comparisons will be presented. Trends in effectiveness endpoints measured over time will be presented graphically by using applicable summary statistics at each time point. If appropriate, statistical tests of the differences in trends may be performed.

8.5.1 Delayed-Start Efficacy Analysis

The delayed-start analysis (Liu-Seifert et al., 2015; Wang et al., 2019) will be performed to evaluate potential disease modifying characteristics of the treatment. Week 24 and Week 48 data will be compared between Group 1 and Group 4. Group 1 (optimal dose treatment) is the early start group and Group 4 (placebo to optimal dose treatment) is the late start group. The analyses will include the following three comparisons:

- At Week 24, the change from baseline of an efficacy variable for Group 1 that achieves statistical significance compared with Group 4
- At Week 48, the change from baseline of an efficacy variable for Group 1 that achieves statistical significance compared with Group 4
- For the change from Week 24 to Week 48 of an efficacy variable, Group 1 is not inferior to Group 4

For continuous efficacy variables such as 6MWD, ANCOVA will be used with baseline 6MWD and randomization stratification factors as covariates. Normality will be examined using the Shapiro-Wilk test. If a normal distribution is rejected, a non-parametric Wilcoxon rank sum test stratified by stratification factors will be used. A multiple imputation method will be used to handle the missing data.

If Week 24 or Week 48 has missing data and subjects are still alive, a standard multiple imputation (MI) will be implemented using a regression model accounting for baseline 6MWD, randomization stratification factors, and if necessary, additional covariates such as demographic variables. For missing 6MWD data due to death, a random sample from the worst 10% change among all subjects will be used.

NT-proBNP is also a continuous variable; therefore, the delayed-start analysis will be performed similar to 6MWD.

The WHO function class improvement is a binary variable; therefore, the delayed-start analysis will be performed by Cochran-Mantel-Haenszel (CMH) test with randomization stratification factors as strata.

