8.1 Introduction: Study Design and Analysis Overview

The LTE is a longitudinal study of the long-term safety and effectiveness of PAH patients treated with AV-101 at different dose levels until being transitioned to the optimal dose of AV-101 which is selected after the completion of the Phase 2b Part of Study AV-101-002 (referred to as the parent study). About 370 subjects (with a maximum of 462 subjects) are expected to start the LTE. LTE subjects may be grouped into the following treatment groups:

- **Group 1 – Optimal Dose Treatment:** Subjects treated with the optimal dose throughout the parent trial and throughout their LTE participation.
- **Group 2 – Non-Optimal Dose Active Treatment, then Optimal Dose Treatment:** Subjects treated with active doses not selected as the optimal dose, who eventually will be treated with the optimal dose when this dose is selected.
- **Group 3 – Placebo to Non-Optimal Dose, then Optimal Dose Treatment:** Subjects originally assigned to the placebo arm during the parent trial then re-randomized to the two non-optimal active groups. Later, they will receive the optimal dose when it is selected.
- **Group 4 – Placebo to Optimal Dose Treatment:** Subjects originally assigned to the placebo arm during the parent trial then either re-randomized or switched to optimal dose.

Further characteristics of these LTE treatment groups are described in [Section 8.3](#).

Among the comparisons to consider are:

- 1) LTE levels and trends among subjects always on the optimal dose Group 1 will be compared in order with those of:
 - Group 4: Placebo to optimal dose treatment
 - Group 3: Placebo to non-optimal dose, then optimal dose treatment
 - Group 2: Non-optimal dose active treatment, then optimal dose treatment
- 2) Levels and trends in LTE safety and effectiveness endpoints for subjects always on the optimal dose (Group 1) will be compared to levels and trends during the parent study among these same subjects. This will be done to document whether the effects of the previous optimal dose on subsequent measures of effectiveness and safety while still undergoing treatment persist, improve, plateau, or dip the longer the duration of the optimal treatment.
- 3) Trends in continuous LTE effectiveness endpoints will be assessed separately for continuous dose intensity and continuous relative dose intensity.

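### The third delayed-start comparison claims non-inferiority, but no margin or confidence-bound rule is stated for any variable, so it cannot be decided as written

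*Combined protocol and SAP*

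**What the plan says.** Section 8.5.1 sets three comparisons between Group 1 (optimal dose throughout) and Group 4 (placebo, then optimal dose). The first two ask for a statistically significant advantage of Group 1 in change from baseline, at Week 24 and at Week 48. The third is a different kind of hypothesis: on the Week 24 to Week 48 change, "Group 1 is not inferior to Group 4".

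The section then gives one set of methods for the whole analysis, without separating the third comparison from the other two:

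- **6MWD:** "ANCOVA will be used with baseline 6MWD and randomization stratification factors as covariates". After a Shapiro-Wilk check, "If a normal distribution is rejected, a non-parametric Wilcoxon rank sum test stratified by stratification factors will be used".
- **NT-proBNP:** handled in the same way as 6MWD. No log transformation is mentioned.
- **WHO functional class improvement:** "the delayed-start analysis will be performed by Cochran-Mantel-Haenszel (CMH) test with randomization stratification factors as strata".

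The parent Section 8.5 supplies the general rules: "Tests of hypotheses in these models will be performed with two-sided tests at 0.05 significance level, adjusted for multiple comparisons", and "Associated 95% confidence intervals for the difference in outcomes in pairwise treatment comparisons will be presented". Neither sentence mentions non-inferiority. On size, Section 8.1 says only this: "About 370 subjects (with a maximum of 462 subjects) are expected to start the LTE". The numbers in Groups 1 and 4 are not given.

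**The concern.** Non-inferiority is shown by ruling out a deficit larger than a stated margin. That needs an estimate, a confidence bound and a margin. For the third comparison the margin is missing for all three variables, and for functional class and the rank-based fallback the named method is a test of no difference.

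The third comparison guards against catch-up. If Group 4 closes the gap once it starts active treatment, the Week 24 advantage looks symptomatic rather than disease-modifying. A safeguard of this kind should be harder to satisfy when data are sparse or noisy. If a non-significant difference were accepted in its place, it would become easier to satisfy, and a claim of disease modification could rest on lack of information.

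**Working it through.** The plan gives no margin, power or sample size for this analysis, so there is no figure of its own to reproduce. The check has two parts.

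**1. What each named method can deliver for the third comparison**

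| Variable | Method in 8.5.1 | Output as named | Decides non-inferiority? |
|---|---|---|---|
| 6MWD, NT-proBNP | ANCOVA (first line) | Adjusted difference and interval | No: no margin |
| 6MWD, NT-proBNP | Stratified Wilcoxon (fallback) | Test of no difference | No: no named estimate, no margin |
| WHO functional class | CMH | Test of no difference | No: no named estimate, no margin |

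The pairwise 95% intervals in Section 8.5 add an interval in principle for each row. They do not add a margin.

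**2. What happens if a non-significant result is taken as non-inferior**

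This reading is not in the plan; it is examined only to size the risk. All inputs are assumptions: SD of the 6MWD change 60 m (varied from 40 to 80 m), 60 or 100 per group, and a true Group 1 deficit d of 10, 15 or 20 m.

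SE = SD × √(2/n)

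P(pass) = Φ(1.96 − d/SE) − Φ(−1.96 − d/SE)

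- n = 100: SE = 60 × √(2/100) = 8.49 m. For d = 15, d/SE = 1.77 and P(pass) = Φ(0.19) − Φ(−3.73) = 0.58.
- n = 60: SE = 60 × √(2/60) = 10.95 m. For d = 15, d/SE = 1.37 and P(pass) = Φ(0.59) − Φ(−3.33) = 0.72.

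| True deficit (SD 60 m) | 100 per group | 60 per group |
|---|---|---|
| 10 m | 78% | 85% |
| 15 m | 58% | 72% |
| 20 m | 35% | 55% |

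For a 15 m deficit with SD from 40 to 80 m, the pass rate runs from 24% to 74% at 100 per group and from 46% to 82% at 60 per group.

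Binary illustration (assumed 20% improved in Group 1 and 30% in Group 4, 100 per group): SE = √(0.20×0.80/100 + 0.30×0.70/100) = 0.0608; 0.10/0.0608 = 1.64; P(pass) = Φ(0.32) − Φ(−3.60) = 0.62.

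For contrast, a rule that the one-sided 97.5% bound must exclude a margin equal to the true deficit passes 2.5% of the time at any group size.

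**Cost of the proper rule.** With an illustrative margin of 15 m, SD 60 m and no true difference, the chance of passing is Φ(15/SE − 1.96): Φ(−0.19) = 42% at 100 per group and Φ(−0.59) = 28% at 60 per group. For 80% power, n per group = 2 × (1.96 + 0.84)² × (60/15)², about 252. In SD units, 80% power needs 393, 175, 99 or 63 per group for margins of 0.2, 0.3, 0.4 or 0.5 SD.

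**The case against.** A reader might infer that the plan will count a non-significant result as non-inferior. The documents do not say so. Section 8.5.1 asks for statistical significance in the first two comparisons and uses different words for the third, so the rule for the third is undefined rather than set to that. The pass rates above therefore describe a possible misreading.

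A reader might also infer that a p-value is the only output available. That is not supported either. ANCOVA is first line for 6MWD and NT-proBNP and yields a difference with an interval, and Section 8.5 promises 95% intervals for pairwise comparisons. This narrows the point but does not remove it: without a margin, an interval cannot decide non-inferiority.

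Three further defences have some force:

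- **Deferral.** Section 8 leaves detail to a SAP, and Section 8.5.1 cites two methodological papers on delayed-start designs. A margin could stand in a separate SAP. None appears in the text supplied, although Section 8.5.1 already fixes the covariates, the normality test, the imputation and the treatment of deaths. Citing a method does not in itself set a margin for these variables in this study.
- **Scope of the figures.** They concern the third comparison alone. The Week 48 superiority comparison stands beside it, so they are not the chance of a false disease-modification conclusion if all three must be met.
- **Importance.** The primary objective is long-term safety, and the delayed-start analysis is not in the endpoint list in Section 2.2. This bears on severity and is accepted.

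**Conclusion.** The point holds: the third comparison is a non-inferiority claim with no margin or confidence-bound criterion for any of its three variables. It cannot be decided as written, and the same is true of any disease-modification conclusion that needs all three comparisons. CMH and the Wilcoxon fallback are unsuitable for this comparison as named. ANCOVA is suitable but incomplete.

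The risk is that the comparison is misread as met on a non-significant test. If that happened, a true 15 m deficit would pass about 58% of the time at 100 per group and 72% at 60 per group. Those figures rest on an assumed SD of 60 m, assumed equal group sizes and a decision rule that the plan does not state.

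Severity: should be fixed. It is not critical, because the analysis is supportive in a safety extension.

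**What to change.** For the third comparison only, replace the difference tests with a one-sided 97.5% confidence bound for Group 1 versus Group 4, taken on the unfavourable side and compared with a stated margin:

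- **6MWD:** the ANCOVA mean difference. If the rank-based fallback is kept, pair it with a stratified Hodges-Lehmann-type interval.
- **NT-proBNP:** ANCOVA on the log scale, reported as a ratio. Lower values are better, so the upper bound is the one to check.
- **WHO functional class:** a stratified (Mantel-Haenszel) risk difference.

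State the margin in one of two ways:

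1. a fixed number for each variable, with its scale and justification; or
2. a pre-set fraction of the Week 24 effect, tested as a single contrast. With D24 and D48 the Group 1 minus Group 4 differences at Weeks 24 and 48 from a common baseline, signed so that positive favours Group 1, and f the fraction to be retained, require the lower bound of D48 − f × D24 to exceed zero. The sampling error of the Week 24 effect is then included. Setting a simple bound against a fraction of the observed Week 24 difference would ignore it.

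Fix the margin before any parent-study results by treatment group are known. "Before unblinding" would be ambiguous, because Section 3.1 ends the blinding of the extension once the optimal dose is chosen from Phase 2b data.

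The cost is SAP wording; no extra data are needed. The downside is that the comparison becomes harder to pass, and power may be low at the group sizes assumed here. That should be stated in advance.

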6.8 Discontinuation of Study Drug and Subject Discontinuation/Withdrawal

6.8.1 Discontinuation of Study Drug

At the time of early study drug discontinuation subjects may elect to (1) discontinue from the study and agree to telephone contacts per the visit schedule, or (2) discontinue from the study, and withdraw consent to be contacted in the future for further collection of study-related data.

For subjects who withdraw from or are withdrawn from taking the study drug, every attempt should be made to follow the subject for long term outcomes. However, if a subject withdraws consent to be contacted, they must complete the Early Discontinuation (ED) Visit within 14 days of AV-101 discontinuation, and then the Safety Follow-Up visits as described in [Section 6.2.2](#) and [6.2.4](#).

For subjects who are lost to follow-up, or who died, Safety Follow-up Visits may not be possible. In any case, the appropriate eCRF section must be completed.

The subject must be discontinued from taking study drug in the event of any of the following:

Examples:

- Enrollment despite violation of an inclusion or exclusion criterion which, in the Investigator’s and/or Sponsor’s opinion, makes discontinuation of the subject necessary.
- Occurrence of an AE/SAE that makes discontinuation of study drug desired or considered necessary by the Investigator and/or the subject.
- Participation in any other interventional study during the duration of this study for which the Investigator considers discontinuation of the AV-101 necessary.
- Occurrence of pregnancy (for further details in case of pregnancy, refer to [Section 7.8](#)).
- If disease activity is considered unacceptably high and treatment escalation beyond permitted medication changes ([Section 5.9.1](#)) is warranted in the view of the Investigator.

- Anaphylaxis, anaphylactoid, or other severe or life-threatening hypersensitivity reactions, based on the Investigator judgement.
- Use of a nonpermitted medicine, as defined in [Section 5.9.2](#). This should first be confirmed with the CRO Medical Monitor before discontinuation of the study drug.
- Noncompliance, judged as significant by the Investigator or Sponsor including noncompliance to the required study considerations, as defined in [Section 5.8](#).
- Surgery considered by the Investigator or Sponsor to be major (see [Section 4.2](#)).

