Visits within a subject form a cluster. Estimated proportions by treatment group and visit will be reported. For Week 24 after optimal dose treatment, the log of odds and proportions of subjects who maintain or improve WHO FC and their 95%CI will be reported by treatment groups. Odd ratios (OR) and 95%CI for subjects always on optimal dose (Group 1) relative to those subjects on always on placebo (Group 4) will be reported. OR and 95%CI among subjects always on optimal dose (Group 1) relative to those of subjects on placebo and then active treatment (Group 3) and OR and 95%CI among subjects always on optimal dose (Group 1) relative to those of subjects on non-optimal dose (Group 2) will also be reported.

4) Time to Clinical Worsening

Time to clinical worsening while in the parent trial and LTE will be based on the first occurrence of any of the following events for each subject.

- Death
- Initiation of parenteral prostanoids
- Hospitalization for worsening PAH
- $\geq 15\%$ decline from baseline in 6MWD and accompanied with progression to or continued WHO FC III or IV symptoms

A subject is evaluated for experiencing any of the above components of clinical worsening throughout the parent trial and LTE study period. Time to clinical worsening is the number of days between the earliest occurrence of the clinical worsening component and the date of the first dose in the parent trial. With treatment groups that change over time intervals, event and censoring will be defined within each time interval. A subject who does not experience any of the clinical worsening component throughout a treatment period/interval is censored and is assigned time to worsening status by the end of the interval. Subjects who are lost to follow-up are typically considered censored. Supplemental analyses will be performed where subjects with an unknown clinical worsening event will be considered to

experience the event and the time to clinical worsening status is the last contact with the subject.

The probability of clinical worsening every 24 weeks after the first dose in the parent trial throughout the LTE will be reported, descriptively as well as based on a Cox model for time to clinical worsening while holding covariates at their means.

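### The Week 48 imputation for living subjects uses no post-baseline information, so the Group 1 versus Group 4 comparison is biased towards whichever group has more worsening-related gaps

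*Combined protocol and SAP*

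**What the plan says.** Section 8.5.1 compares Group 1 (early start) with Group 4 (late start) in three steps: superiority at Week 24; superiority at Week 48 ("At Week 48, the change from baseline of an efficacy variable for Group 1 that achieves statistical significance compared with Group 4"); and non-inferiority over the second period ("For the change from Week 24 to Week 48 of an efficacy variable, Group 1 is not inferior to Group 4").

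Missing 6MWD is handled by vital status alone. The rule for the living reads: "If Week 24 or Week 48 has missing data and subjects are still alive, a standard multiple imputation (MI) will be implemented". The rule for deaths reads: "For missing 6MWD data due to death, a random sample from the worst 10% change among all subjects will be used". As to which variables inform the draws for the living, the section describes the model only as one "accounting for baseline 6MWD, randomization stratification factors, and if necessary, additional covariates such as demographic variables". NT-proBNP is to be analysed in a similar way. The section gives no sensitivity analysis.

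Three other places bear on this:
- **Section 6.8.1.** One ground for stopping study drug begins "If disease activity is considered unacceptably high and treatment escalation beyond permitted medication changes", where the investigator judges that escalation to be warranted. A subject who stops may "discontinue from the study and agree to telephone contacts per the visit schedule", or may also withdraw consent to further contact.
- **Table 1.** A 6MWT is scheduled at LTE Weeks 4, 12 and 24 and at the Early Discontinuation visit. Footnote 2 lets a subject who cannot attend that visit complete it by telephone.
- **Section 8.5.2, item 4.** "Hospitalization for worsening PAH" and the start of parenteral prostanoids sit in one composite with death.

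**The concern.** Standard multiple imputation is valid if, given the variables in the model, the missing values resemble the observed ones. Here some gaps arise because the disease got worse after baseline. The evidence of that worsening (interim walks, the discontinuation walk, clinical-worsening status) is collected but is not in the stated model. Such a subject is given a value drawn from what baseline would predict for someone who kept walking.

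The delayed-start analysis is the plan's test of disease modification, and two of its three legs depend on Week 48. If worsening-related gaps are unequal between the groups, both legs are distorted: a loss of benefit can be concealed in Group 1, or a genuine advantage of Group 1 can be concealed because failures in Group 4 are filled in too favourably.

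**Working it through.** The plan has no figure to reproduce. It states no SD, missing-data rate, group sizes or non-inferiority margin for this analysis, so every number below rests on a labelled assumption. Week 48 is read as counted from parent baseline, that is LTE Week 24; Section 8.5.1 does not say so.

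**Step 1. Where the gaps can fall.** LTE entry requires completion of the parent study (Section 4.1), and the parent Week 24 visit is the LTE baseline visit (Section 6). Subjects who stopped for disease activity before Week 24 are therefore not in Groups 1 or 4. Worsening-related gaps concentrate at Week 48.

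**Step 2. Size per subject, on the plan's own scale.** For a normal distribution, the mean of the worst 10% lies φ(z₀.₁₀)/0.10 = 1.755 SD below the overall mean. With an assumed SD of change of 45, 60 or 75 m:
- 1.755 × 45 = 79 m
- 1.755 × 60 = 105 m
- 1.755 × 75 = 132 m

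**Step 3. Bias in the group difference.** Let p1 and p4 be the shares of living subjects with a worsening-related gap, and W their extra loss. If imputation treats them like observed subjects of their own group, the bias in Group 1 minus Group 4 is (p1 − p4) × W. With W from Step 2 at SD 45 and 75 m:
- 8% vs 4%: 0.04 × 79 to 0.04 × 132 = 3.2 to 5.3 m in favour of Group 1
- 4% vs 8%: the same size, against Group 1
- equal shares: 0

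**Step 4. Effect on the non-inferiority decision.** Simulation under harsher assumptions, none from the documents: 90 per group, SD 45 m for each 24-week change, W = 80 m, margin 20 m, one-sided 0.025, 10 imputations with Rubin's rules, ANCOVA, 800 runs per case. Entries are the probability of declaring non-inferiority.

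| True difference | Gaps, Group 1 / Group 4 | Listed covariates only | Plus treatment group | Plus group and Week 24 6MWD | Worst-10% draw |
|---|---|---|---|---|---|
| −20 m | 15% / 5% | 0.091 | 0.160 | 0.216 | 0.054 |
| −20 m | 10% / 10% | 0.013 | 0.016 | 0.024 | 0.035 |
| −20 m | 5% / 15% | 0.000 | 0.000 | 0.000 | 0.050 |
| 0 m | 15% / 5% | 0.916 | 0.938 | 0.974 | 0.743 |
| 0 m | 10% / 10% | 0.664 | 0.716 | 0.810 | 0.782 |
| 0 m | 5% / 15% | 0.246 | 0.255 | 0.404 | 0.776 |

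Monte Carlo error is roughly 0.005 to 0.017. In the first row, with treatment group in the model, the mean estimate was −12.0 m against a true −20 m. That bias of 8 m equals (0.15 − 0.05) × 80, as Step 3 predicts.

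**Step 5. What post-baseline data can recover.** If the added variables capture a fraction r of the loss, the remaining bias is (1 − r) × (p1 − p4) × W. Week 24 6MWD alone captures almost none of it, because the loss comes later (mean estimate −11.7 m in the same case). It does improve precision: with equal shares the standard error falls from 8.1 to 7.2 m. In a further assumed simulation, with 12% vs 4% missing, adding post-baseline data cut the bias from about 5–6 m to 1.8 m. That is r between 1 − 1.8/5 = 0.64 and 1 − 1.8/6 = 0.70. It is indicative only, since r depends on how many interim and discontinuation walks are obtained.

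**The case against.** **Direction.** A reader might infer that the rule systematically favours the non-inferiority leg. The documents do not support that. The sign follows p1 − p4, which they do not give. Both groups take the optimal dose in this window; Group 1 has already completed 24 weeks on it, while Group 4 is receiving AV-101 for the first time. More failures in Group 4 are at least as plausible, and the rule then works against Group 1.

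**Worsening is not the same as missingness.** A reader might also infer that everyone who worsens lacks a Week 48 walk. That is too strong. Licensed background PAH therapy is allowed (Section 1.3) and new PAH therapy may be added (Section 5.9.1.1), inhaled prostacyclins excepted. Neither a PAH hospitalisation nor the start of parenteral prostanoids is itself listed as a reason to stop. Many such subjects can stay and walk. The gap is real for those who stop, but the affected share may be small.

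**The imputed value is not a flat average.** Regression imputation draws a value predicted from covariates plus residual error. The covariate list is also open-ended, and Section 8 defers detail to a SAP. This stands, but the only further examples named are demographic, and the text available gives no other imputation rule.

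**Other analyses see these failures.** Time to clinical worsening counts them directly, with a supplemental analysis treating unknown status as an event. The repeated-measures model in Section 8.5.2 uses interim walks. Both help the study as a whole, but neither corrects the delayed-start comparison.

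**The metre figures.** They measure distance from the plan's death score and equal bias only if these subjects truly belong there. They also do not carry over directly if non-normality triggers the stratified Wilcoxon test.

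**The worst-10% score as the main rule.** That would be a choice of estimand. In Step 4 it reduces dependence on which group fails more, but at the margin its error is 0.035 to 0.054, above 0.025 throughout. This supports using it as a sensitivity analysis and not as the main rule.

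**Conclusion.** The concern holds in a bounded form. The stated model for living subjects contains no post-baseline information, although subjects who stop AV-101 for disease activity have no later scheduled clinic walk. The Week 48 and Week 24-to-48 comparisons are therefore biased whenever worsening-related gaps differ between Groups 1 and 4, in favour of the group with more of them. The size is about 3 to 5 m for an 8% vs 4% imbalance, assuming SD 45 to 75 m, normal changes, and that these subjects belong in the worst 10%; it is near zero with equal shares.

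The Week 24 comparison is little affected (Step 1). No overall direction for the non-inferiority leg can be claimed: the 0.160 false-positive rate in Step 4 needs an assumed 15% vs 5% imbalance and an assumed margin. This is a worthwhile, inexpensive improvement and does not invalidate the analysis.

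**What to change.** 1. In Section 8.5.1, specify the Week 48 imputation model for living subjects to include treatment group, Week 24 6MWD, interim LTE walks, the Early Discontinuation visit 6MWD and clinical-worsening status, alongside the covariates already listed. Do the same for NT-proBNP with its own interim values. Adding Week 24 alone is not enough.
2. Prespecify a sensitivity analysis that applies the existing worst-10% rule to Week 48 values missing in living subjects after a clinical-worsening event or after discontinuation for disease activity.
3. State that Week 48 is counted from parent baseline, if that is what is meant, so that it is clear which LTE walks are interim.

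Cost: SAP-level wording, a slightly more complex imputation model and one derived reason-for-missing flag. No added visits are needed: the walks and clinical-worsening status are scheduled in Table 1, and discontinuation reasons are reported under Section 8.4. Group means may become less favourable. The worsening term will be imprecise if few subjects both worsen and still walk at Week 48, which is why the sensitivity analysis is needed as well.
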